8.2.2 DEFINITION OF DOSE-LIMITING TOXICITIES (DLTs)

Dose-limiting toxicities (DLTs) are defined as AEs occurring during the first 7 days after NB01 application that are not due to the subject's underlying disease, are not clearly attributable to other etiologies, and meet any of the following toxicity criteria:

Dermatologic Toxicities:

- Skin Dryness Score of 3
- Skin Peeling Score of 3
- Irritant/Allergic Contact Score of 3
- Hyperpigmentation Score of 3
- Skin Erythema Score of 3
- Exacerbation of disease determined by an increase in IGA score 1 point beyond baseline screening score

Ocular Toxicities:

- Conjunctival injection score of 3
- Eye irritation score of 3

Mucosal Toxicities:

- Mucosal Irritation Score of 3

If any systemic toxicities develop, the Sponsor will pause the study for further review before proceeding. If 2 or more subjects experience a DLT, or in the event of an SAE that is at least possibly-related to study treatment, the Sponsor will pause the study to discuss with the PI and regulatory authorities, if needed.

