^h BPO gel should be applied for at least 5 days, in the AM immediately after the AM Cetaphil® wash. Final BPO pre-treatment should be completed at least 24 hours prior to PI application of NB01, thus final BPO application will most likely occur in the AM prior to the Day 1 (0H) visit.

ⁱ Trial subjects will note date and time of each BPO pre-treatment and Cetaphil® wash for the Screening period, and the date and time for each Cetaphil® wash during the 28-day treatment period.

^j Subjects will remain at the clinic for at least 30 minutes post application at T0H to be assessed for adverse reactions.

^k AEs will be assessed from the time of e-consent.

^l On Day 1, after baseline measurements have been obtained, subjects will then wash at the clinic before NB01 is applied by the PI.

^m Subjects initiate BID washing of their faces after waiting 24 hours from T0H, or 24H (Study Day 2). Subjects should withhold morning wash and morning facial shaving at home until they arrive at the clinic all clinic days. Once clinic day sampling has occurred, the subject may wash at the clinic. The only exception being that the subject should wash their face in the office with Cetaphil®, prior to the Day 2 Bioré® Strip follicular engraftment sampling

ⁿ Study procedures are completed as needed, as clinically indicated, for unscheduled study visits.

^o The EOS Visit should be completed on Day 28, or prior to the initiation of new anti-acne therapy. Should the subject discontinue the study early, the EOS should be scheduled and completed as soon as possible.

^p No other cleansers can be used throughout the study, from the Screening Visit to Day 28/EOS.

^q Subjects will hold the PM Cetaphil® wash prior to the Day 1 study drug application.

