8 STUDY ASSESSMENTS AND PROCEDURES

8.1 SAFETY AND OTHER ASSESSMENTS

Subjects will come to the clinic for the following protocol-specified visits: Screening, 0H (+2-day window), 6H, 24H, 48H, 7 days (± 1 -day window) and 28 days (± 3 -day window) days post application. It is important that the 6H, 24H and 48H visits be on approximately on time (± 2 -hour window) to ensure engraftment can be properly assessed.

Screening

Once the subject has provided consent to participate, the following required procedures will be completed at the Screening Visit:

- Review of subject eligibility based on inclusion and exclusion criteria
- Vitals: Blood pressure, heart rate and temperature
- Labs:
 - CBC
 - Urine dipstick pregnancy test (females of childbearing potential)
- Screening IGA score and total lesion count
- Screening porphyrin and sebum levels (Pear 3D)
- Screening photographs (Pear 3D)
- Screening pH (pH meter)
- A pre-BPO cheek swab sample will be procured
- Pre- Bioré® sampling facial wash with Cetaphil®
- A pre-BPO Bioré® sample will be obtained

The following procedures will be completed within the Screening Period:

- Subjects will initiate 5-day, at-home pre-treatment with a 5.0% BPO gel daily application to the face (<https://www.perrigo.com/business/product.aspx?ID=88&let=B> Perrigo 5% BP Aqueous Gel) at the same time each day, immediately after the AM Cetaphil® wash. The final BPO gel application should be at least 24 hours prior to study drug application (and therefore likely the morning before the Day 1 (0H) visit)
- Subjects will initiate a 5-day at-home BID Cetaphil® wash at the same time each day, with the PM wash to be held the day before the Day 1 (0H) visit. No other cleansers can be used throughout the study, from the Screening Visit to Day 28/EOS.
- Subjects will complete an in-home patient e-diary during the pre-treatment period

Once the subject's eligibility has been confirmed and pre-treatment BPO period completed, the subject will be enrolled into the study and initiate on-study procedures, including ongoing patient e-diary for Cetaphil® washes.

Treatment Period

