8.2.3 TIME PERIOD AND FREQUENCY FOR EVENT ASSESSMENT AND FOLLOW-UP

Subjects will be monitored for safety at all study visits: Screening, 0H, 6H, 24H, 48H, 7 days and 28

days after initial application.

All AEs, including local and systemic reactions not meeting the criteria for SAEs, will be captured on the appropriate CRF/eCRF. Information to be collected includes:

- event description
- time of onset
- clinician's assessment of severity
- relationship to study product (assessed only by those with the training and authority to make a diagnosis)
- time of resolution/stabilization of the event.

All AEs occurring while on study must be documented appropriately regardless of relationship. All AEs will be followed to adequate resolution.

Any medical condition that is present at the time that the participant is screened will be considered as baseline and not reported as an AE. However, if the study participant's condition deteriorates at any time during the study, it will be recorded as an AE, specifically, worsening of the pre-existing condition.

Changes in the severity of an AE will be documented to allow an assessment of the duration of the event at each level of severity to be performed. AEs characterized as intermittent require documentation of event onset and duration of each episode.

The study site will record all reportable events with start dates occurring any time after informed e-consent is obtained until 7 (for non-serious AEs) or 30 days (for SAEs) after the last day of study participation. At each study visit, the PI will inquire about the occurrence of AE/SAE since the last visit. Events will be followed for outcome information until resolution or stabilization.

SEVERITY

A clinical determination will be made of the intensity of an AE. The severity assessment for a clinical AE must be completed using the following definitions as guidelines:

Mild; asymptomatic or mild symptoms; easily tolerated; clinical or diagnostic observations only; intervention not indicated.
Moderate; minimal. local. or noninvasive intervention indicated; limiting age□appropriate activities of daily living.
Severe or medically significant but not immediately life-threatening; hospitalization or prolongation of hospitalization indicated; disabling; limiting self-care activities of daily living.
Life-threatening consequences; urgent intervention indicated.
Death due to AE

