9 EFFICACY

9.1 CONSIDERATIONS FOR EFFICACY

- **Tolerability Scale for Topical Acne Treatments, all visits:**

Reference: ClinTrials.gov: [Investigator Assessment Tolerability Scoring: A Study to Evaluate Tolerability of Two Topical Drug Products in the Treatment of Acne](#). Please see Appendix C of this protocol.

1. Skin Dryness Score: Investigator Assessment of Tolerability Scale (0 = None; 1 = Slight; 2 = Moderate; 3 = Intense)
2. Skin Peeling Score: Investigator Assessment of Tolerability Scale (0 = None; 1 = Slight; 2 = Moderate; 3 = Intense)
3. Irritant/Allergic Contact Dermatitis Score: Investigator Assessment of Tolerability Scale (0 = None; 1 = Slight; 2 = Moderate; 3 = Intense)
4. Hyperpigmentation Score: Investigator Assessment of Tolerability Scale (0 = None; 1 = Slight; 2 = Moderate; 3 = Intense)
5. Ocular Irritation: Investigator Assessment of Tolerability Scale (0 = None; 1 = Slight; 2 = Moderate; 3 = Intense)

6. Conjunctival Injection: Investigator Assessment of Tolerability Scale (0 = None; 1 = Slight; 2 = Moderate; 3 = Intense)
 7. Mucosal Toxicity: Investigator Assessment of Tolerability Scale (0 = None; 1 = Slight; 2 = Moderate; 3 = Intense)
 8. Skin Erythema Score: Investigator Assessment of Tolerability Scale (0 = None; 1 = Slight; 2 = Moderate; 3 = Intense)
- **Assessment of disease status using IGA Score and Acne Lesion Count**
 - **Engraftment and Dose Schedule Determination**

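### A reaction that comes and goes between the 48H and 7-day visits has no stated route into the DLT count unless it is seen at an unscheduled visit; a worst-score entry would be a cheap remedy

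*Combined protocol and SAP*

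**What the plan says.** **DLT criteria.** Section 8.2.2 sets the window: "Dose-limiting toxicities (DLTs) are defined as AEs occurring during the first 7 days after NB01 application". The event must not be due to the underlying disease or clearly attributable to another cause, and must meet one of nine criteria. Eight are the top score on a tolerability item (five skin, two ocular, one mucosal), for example "Skin Erythema Score of 3". The ninth is "Exacerbation of disease determined by an increase in IGA score 1 point beyond baseline screening score".

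**When these are rated.** Section 9.1 lists the 0-3 scale under "Tolerability Scale for Topical Acne Treatments, all visits". Section 8.1 gives the visits: "Subjects will come to the clinic for the following protocol-specified visits: Screening, 0H (+2-day window), 6H, 24H, 48H, 7 days", followed by 28 days. The Schedule of Events marks the tolerability scale and the IGA at each of them. It also marks both in the Unscheduled Visit column, to be done as clinically indicated (footnote n).

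**How an AE is graded.** Section 8.2.3: "The severity assessment for a clinical AE must be completed using the following definitions as guidelines". Five levels follow, from mild to death.

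**What the e-diary holds.** Schedule of Events, footnote i: "Trial subjects will note date and time of each BPO pre-treatment and Cetaphil® wash for the Screening period", and wash times during the 28-day treatment period. No symptom entry is described there or in Section 5.5.

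**What the count is used for.** Under Section 4.1, fewer than 2 DLTs in the first five subjects leads to a Dose Escalation Meeting between the investigator and the Medical Monitor on opening Cohort 2. Section 8.2.2 pauses the study if 2 or more subjects have a DLT.

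**The concern.** Eight of the nine criteria depend on a score that an investigator gives in clinic, and the ninth on an IGA that is also rated in clinic. Both follow the same schedule, which is dense to 48H and then silent until the 7-day visit. No contact is scheduled in that interval and no diary item would flag a reaction. Section 6.3.1 lets subjects resume or introduce moisturizers, sunscreens and makeup after the Day 3 visit, so new exposures can begin just as scheduled scoring stops.

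Under Section 5.5, a subject who completes the safety procedures through Day 7 is DLT-evaluable. A subject whose reaction was intense on Day 4 and gone by Day 7 can thus enter the count as evaluable and DLT-free. Missed events can only lower the count, which pushes the fewer-than-2 gate towards a tenfold higher dose. With five subjects, one event can decide it. Section 2.2 says there are no in vivo data for this product, so the documents give no basis for assuming that reactions will show by 48H.

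**Working it through.** The plan states no operating characteristic or sample-size figure (Section 10.2), so there is none to reproduce. The check covers the schedule, the route of a recalled reaction, and an illustration.

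**1. Length of the gap.** Inputs: a DLT window of 7 days = 168 h (Section 8.2.2); visits at 0, 6, 24, 48 and 168 h; windows of ±2 h on 48H and ±1 day on the 7-day visit (Section 8.1).

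- Intervals between ratings: 6, 18, 24 and 120 h.
- Nominal share: (168 − 48)/168 = 120/168 = 71.4%.
- With ±2 h on 48H: 168 − 50 = 118 h (70.2%) to 168 − 46 = 122 h (72.6%).
- 7-day visit a day early (144 h): 94 to 98 h between visits, plus 24 h of the window after the last rating. The total is again 118 to 122 h.
- 7-day visit a day late (192 h): up to 192 − 46 = 146 h between visits, but at most 122 h of that lies in the window.
- Schedule of Events labels (0H = Day 1, 48H = Day 3, then Day 7 = 144 h): 96 h between visits, or 96/168 = 57.1%, plus 24 h after the Day 7 rating if the window runs to 168 h. If the window is taken to end at 144 h, the share is 96/144 = 66.7%.

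**2. What happens to a reaction in the gap.**

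| Situation | What the documents provide |
|---|---|
| Still present at the 7-day visit | 0-3 score given; DLT criteria can be applied |
| Reported and seen at an unscheduled visit | Tolerability scale and IGA are marked; DLT criteria can be applied |
| Resolved and recalled at Day 7 | AE recorded with onset, resolution and a mild-to-death grade; no rule for giving a 0-3 score |

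The two scales are not mapped. Severe in Section 8.2.3 is tied to hospitalization, disability or limited self-care, so a reaction that would score 3 (intense) could be entered as a mild or moderate AE. The AE form alone would not show that a DLT criterion had been met.

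**3. Illustration (all inputs assumed).** For a reaction of fixed duration d hours (at most 120) starting uniformly in the 120 h gap, the chance that it is still present at 168 h is d/120: 20% for 24 h, 40% for 48 h, 60% for 72 h.

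Let p be the true share of subjects with a DLT and m the share of those missed by every route. With r = p(1 − m), P(fewer than 2 recorded in 5) = (1 − r)^5 + 5r(1 − r)^4. For p = 0.30 and m = 0.50, r = 0.15, giving 0.4437 + 0.3915 = 0.835.

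| True rate p | None missed | 25% missed | 50% missed |
|---|---|---|---|
| 0.10 | 0.919 | 0.952 | 0.977 |
| 0.30 | 0.528 | 0.685 | 0.835 |
| 0.50 | 0.188 | 0.381 | 0.633 |

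The effect is small when DLTs are rare and large when they are common, which is when the gate matters most.

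**The case against.** The strongest reply is that the protocol already has ways to catch such a reaction. Section 8.2.2 does not require the score to come from a scheduled visit. Unscheduled visits carry both ratings. Section 8.2.1 accepts AEs volunteered between visits, allows directed questioning and examination, and makes the 0-3 scale one of the means by which the investigator determines AEs. Section 8.2.3 requires a question about events since the last visit. Escalation is not automatic either: the investigator and Medical Monitor must meet (Sections 4.1 and 11.1.6), Cohort 2 follows AE evaluation (Section 10.3), and possibly related SAEs and systemic toxicities are separate triggers (Sections 8.1 and 8.2.2).

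All of this stands, and it rules out several stronger readings that a reader might infer:

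- That a reaction in the gap cannot count, or is by definition not a DLT. The documents are silent on retrospective scoring; they do not exclude it.
- That an unscheduled visit happens only at the subject's request. Footnote n says only that its procedures are done as clinically indicated.
- That 71% of DLTs would be missed. The figure is a share of time.

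What the reply does not supply is a rule for the reaction that is recalled but no longer visible. The review meeting can see that AE, but without a 0-3 score it cannot tell whether the plan's own criterion was met.

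**Conclusion.** The point holds as a gap in how a primary safety outcome is captured, and it is cheap to close. No rating is scheduled for nominally 120 of the 168 hours (118 to 122 h with the 48H window; 96 h between visits on the Schedule of Events labels). A score-3 reaction confined to that interval reaches the 0-3 scale if it is seen at an unscheduled visit. For one that is only recalled, the documents state no route to the DLT count. Any resulting error runs one way, towards fewer recorded DLTs.

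How often this would occur cannot be derived from the documents. The probabilities in the working rest on assumed event rates and missed shares, with at most one counted DLT per subject, and they show sensitivity only. The investigator and Medical Monitor review limits the consequence but does not remove it.

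**What to change.** 1. At each post-application visit through Day 7, record on the CRF two tolerability scores per item: the current score and the worst since the last visit, both on the existing 0-3 scale.
2. Present both to the Dose Escalation Meeting.
3. Reconcile Section 8.2.2 with Section 8.2.3 so that the protocol states how a reaction resolved before the visit is assessed against the existing DLT criteria, including the IGA criterion, which has the same scheduled gap. How that is settled is for the sponsor and the investigator. The threshold, the 7-day window and the fewer-than-2 gate need not change.
4. Optionally, add one daily yes/no item on skin, eye or mouth reactions to the existing e-diary for Days 1-7, to support recall.

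The cost is one CRF column, a short text change and, if wanted, one diary item, with no added scheduled visit. The downside is that worst-since-last-visit scores rely partly on recall, and a few more DLTs may be counted. Keeping the two scores in separate fields lets the meeting see which rest on recall.

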4 STUDY DESIGN

4.1 OVERALL DESIGN

This is a first human, single-center, dose escalation, open-label trial of a single application of topically delivered NB01 in subjects with moderate, non-cyclical facial acne.

Ten subjects will be assigned to 1 of 2 dose cohorts in a stepwise fashion after a 5-day pre-treatment with 5.0% daily BPO gel (<https://www.perrigo.com/business/product.aspx?ID=88&let=B> Perrigo 5% BP Aqueous Gel).

- Cohort 1: 10⁵ CFU/cm² NB01
- Cohort 2: 10⁶ CFU/cm² NB01

This will be ascending dose finding whereby 5 initial subjects will be assigned to Cohort 1 to receive a single application of 10^5 CFU/cm² to the facial skin of the nose/cheek. If there are less than 2 dose-limiting toxicities (DLTs) during the 7-day safety assessment, a Dose Escalation Meeting will be held between the PI and the Sponsor Medical Monitor to determine whether Cohort 2 will be opened to enrollment.

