5.5 ENROLLMENT PROCEDURES AND TREATMENT ASSIGNMENT

The screening date will be defined as the date the subject signs the ICF. Subjects will be screened within 5 days (+2 days) of enrollment to determine eligibility for participation in the study. Screening laboratory results for hematology (Complete Blood Counts [CBC]) should be obtained from the local laboratory. Screening procedures (Section 8.1) will be performed and documented, at the end of which the clinical site will complete subject and visit information on the Enrollment Request Form (ERF) for Sponsor approval. Approved subjects who meet all inclusion criteria and none of the exclusion criteria may be enrolled into the trial.

It is the responsibility of the PI to ensure that subjects are eligible for the study prior to enrolling into the study. Subjects who do not enroll within the Screening Period will be screen failed. A subject will be considered enrolled once he or she has signed the ICF, met all inclusion/exclusion criteria, executed all screening visit measurements, including daily BPO therapy, and received Sponsor approval to participate.

This is an open-label study. Subjects will be assigned a unique Screening Number at the time of e-consent. Subjects who have met all eligibility criteria will initiate an at-home daily application of a 5.0% BPO gel treatment, and BID Cetaphil® wash and complete an electronic, in-home patient diary (e-diary). They will return to the clinic on Day 1 to perform baseline assessments. Day 1 is defined as the date the first application of NB01 will occur. All baseline tests and procedures must be completed prior to the application of the first dose of study drug on Day 1, time point 0H. Once eligibility is confirmed, subjects will be assigned a unique Subject ID number and be assigned to a cohort. Once a Subject ID has been assigned to a subject, it will not be reassigned to another subject.

Each on-study visit will be scheduled relative to Day 1 0H. Enrolled subjects will complete an in-home e-diary to capture at home Cetaphil® washing through the end of the study. Visits will follow the SOE table and protocol section 8.1. The ERF and additional details can be located in the Study Reference Manual for the trial.

Re-Screening of Subjects

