7 STUDY INTERVENTION DISCONTINUATION AND PARTICIPANT DISCONTINUATION/WITHDRAWAL

7.1 PARTICIPANT DISCONTINUATION/WITHDRAWAL FROM THE STUDY

Participants are free to withdraw from participation in the study at any time.

Participants will remain in the study through Day 28, or may discontinue early if any of the following criteria are met:

- PI decision
- Subject withdrawal of consent
- Subject is lost to follow-up
- Unacceptable Toxicity (exacerbation of IGA 1 point higher than baseline)
- Sponsor termination of the trial

A PI may discontinue a participant from the study for the following reasons:

- Pregnancy
- Failure to comply with the study procedures, including inability to receive study drug or missing study appointments
- If any clinical AE, laboratory abnormality, or other medical condition or situation occurs such that continued participation in the study would not be in the best interest of the participant
- Disease progression, which requires discontinuation of the study intervention

The reason for participant discontinuation from the study will be recorded on the Case Report Form (CRF)/electronic CRF (eCRF).

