Post BPO-period porphyrin level, sebum production, pH, IGA assessment, total lesion count, and photos will be obtained on Day 1, followed by the engraftment assay. Urine dipstick pregnancy test will be obtained for females of childbearing potential. After these measurements are obtained, subjects will wash their face with Cetaphil® (Galderma) in the office and then the single study drug dose will be applied by the PI (OH). The application should take place at least 24 hours after the last morning BPO application. The PI will apply drug once (time point 0H) to the face: cheek/nose (approximately 50 cm²) to Cohort 1 subjects. If there are less than 2 DLTs and no possibly-related SAEs in Cohort 1 during the 7-day safety assessment, the remaining subjects will be enrolled into Cohort 2 to receive single application to the face: cheek/nose. Subjects will then be monitored for at least 30 minutes after the application for any allergic or anaphylactic reactions. Subjects should not wash or shave their face again until the 24H sampling is completed with the exception that the Bioré® strip follicular assessment will be obtained after washing face with Cetaphil® in office. Subjects may then initiate facial cleansing with Cetaphil® wash BID. However, for all office visit days, subjects should hold the morning wash and morning shaving until visit samples have been obtained.

Engraftment sample procurement: Samples for engraftment will be obtained using a Fab-Swab Filtered Air Breathable Sterile Flocked Collection Device (PurFlock® Ultra-Puritan Diagnostics). The face will be quartered into left lateral, left medial, right lateral, right medial for sampling procurement, with mid pupillary line splitting medial and lateral quarters and midline forehead/nose splitting medial quarters. Each sampling will only test a quarter of the face to ensure that sampling post drug application do not remove study drug prior to the next sampling time point and to improve standardization of sampling area. To obtain samples, the swabs should be pressed firmly and rubbed over the designated quadrant for that sample time-point with occasional rotation of the swab for a duration of a minimum of 30 seconds. Please refer to the Laboratory Manual for detailed instructions.

Subjects will be monitored for safety at all study visits: 0H, 6H, 24H, 48H, 7 days and 28 days after the initial application.

Vitals will be taken at study visits: Screening, 24H, 7 days, and 28 days.

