The following will be completed at all office study visits (0H, 6H, 24H, 48H, 7 days, and 28 days), unless otherwise specified:

- Assess for any new or existing AEs or SAEs
- Review concomitant medications
- Obtain cheek samples for
 - Porphyrin presence (Pear 3D)
 - Sebum production (Pear 3D)
- Photography (Pear 3D)
- IGA
- Absolute lesion counts
- pH of skin (pH meter)
- Assess engraftment via Fab-Swab Filtered Air Breathable Sterile Flocked Collection Device (PurFlock® Ultra-Puritan Diagnostics) (TaqMan® assay)
- Assess follicular engraftment via Bioré® strip (TaqMan® assay, at 24H only)
- Urine dipstick pregnancy test (females of childbearing potential, at 0H and Day 28 only)

NOTE: Additional vital signs and CBC may be repeated, as clinically indicated.

End of Study (EOS)

Subjects will remain in the study through Day 28, or may discontinue early, as described in protocol section [7.1](#). Subjects will have completed the study upon conclusion of the Day 28/EOS visit procedures. Subjects who discontinue prior to Day 28 should have the EOS visit scheduled as soon as possible, in

order to complete final safety assessments, prior to discontinuation from the study.

Early Discontinuation of Subjects

Subjects may voluntarily withdraw from the study at any time. A subject's participation in the study may be terminated if it is deemed by the PI or Sponsor that it is unsafe for the subject to continue in the study. Subjects who discontinue prior to completing the DLT evaluation period (i.e., prior to completion of Day 7 procedures) for reasons other than a DLT, will be replaced.

Notification of early subject discontinuation from the study and the reason for discontinuation will be made to Sponsor and will be clearly documented on the appropriate eCRF.

Study Termination

The study may be stopped at his/her study site at any time by the site PI. Sponsor may stop the study (and/or the study site) for any reason with appropriate notification. Both the Sponsor and the PI reserve the right to terminate the study at any time. Should this be necessary, both parties will arrange discontinuation procedures and notify the appropriate regulatory authority(ies), and IRBs. In terminating the study, Naked Biome and the PI will assure that adequate consideration is given to the protection of the subjects' interests.

Adverse Events (AEs)

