11.1.6 SAFETY OVERSIGHT

Safety oversight will be under the direction of the Principal Investigator (PI) and the Sponsor Medical Monitor (MM).

Once the first 5 safety-evaluable subjects in Cohort 1 complete the Day 7 assessments, the PI and MM will convene a Dose Escalation call and determine whether to open enrollment into Cohort 2. The decisions will be documented in minutes, and the minutes on file as part of Sponsor's central study record.

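### The two-subject pause in Section 8.2.2 counts non-serious local toxicity only in the first 7 days, so later local events meet no written study-level criterion while Cohort 2 may still be being dosed

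*Combined protocol and SAP*

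**What the plan says.** Section 8.2.2 sets the window: "Dose-limiting toxicities (DLTs) are defined as AEs occurring during the first 7 days after NB01 application". A DLT must also not be due to the underlying disease or clearly attributable to another cause. It must meet a listed criterion: a tolerability score of 3 on a dermatologic, ocular or mucosal item, or an IGA score one point above screening.

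The same section names three pause triggers. One is any systemic toxicity. The other two are in one sentence: "If 2 or more subjects experience a DLT, or in the event of an SAE that is at least possibly-related to study treatment". The systemic and SAE triggers carry no time limit.

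Opening Cohort 2 rests on the same window. Section 8.1 puts it as "If there are less than 2 DLTs and no possibly-related SAEs in Cohort 1 during the 7-day safety assessment". Section 4.1 sends a result of fewer than two DLTs to a Dose Escalation Meeting "to determine whether Cohort 2 will be opened to enrollment". Section 11.1.6 times that call: "Once the first 5 safety-evaluable subjects in Cohort 1 complete the Day 7 assessments". Section 6.1.1 also uses the Cohort 1 DLT count.

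Follow-up runs to Day 28, with IGA and tolerability scored there under the Schedule of Events. On day numbering, Section 5.5 says "Day 1 is defined as the date the first application of NB01 will occur".

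**The concern.** This is a first-in-human, open-label trial of a live organism intended to populate the skin, and the second cohort receives 10^6 rather than 10^5 CFU/cm². The protocol already regards a one-point IGA rise, or a local score of 3, as serious enough that two affected subjects should halt dosing for review. That holds if onset is on Day 6. If the same findings appear on Day 10 and are attributed to treatment, no written criterion responds, however many subjects are affected.

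The individual rules do not fill the gap. Section 7.1 (one-point IGA rise) and Section 8.2.1 (severe local toxicity, at the PI's judgement) let an affected subject leave the trial. NB01 is applied once, so that subject has no further dose to withhold. Only a study-level hold protects subjects who have not yet been dosed.

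**Working it through.** The plan states no error rate or operating figure for its pause rule, so there is none to reproduce. The check is a reading of the rules followed by day arithmetic.

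**Which rule catches a late, non-serious local event?**

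- Systemic toxicity (8.2.2): no. The section lists dermatologic, ocular and mucosal scores separately, and Section 8.2.3 distinguishes local from systemic reactions.
- Possibly related SAE (8.2.2): only if the event is serious. A late local event judged an important medical event under Section 8.2.1 would qualify, and is outside this point.
- Two subjects with a DLT (8.2.2): no, because of the 7-day limit.
- Cohort 2 gate (4.1, 6.1.1, 8.1, 11.1.6): it uses DLT counts and the Day 7 assessment.
- Subject discontinuation (7.1, 8.2.1): acts on the individual only.
- Study termination (8.1): discretionary, with no criterion.

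**Where the window ends.** Application is on Day 1. Seven full days later is 1 + 7 = Day 8; counting Day 1 as the first day gives Day 7. Day 9 is outside on either count. Of the five scheduled post-dose visits (6H, 24H, 48H, 7 days, 28 days), one lies outside the window: Day 28.

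**Possible overlap of the cohorts.** Let g be the days from the last Cohort 1 application to the first Cohort 2 application.

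- If Cohort 2 subjects are screened and pre-treated in parallel, g is about 7.
- If screening starts only at the last Cohort 1 Day 7 visit, g = 7 + 5 days of BPO = 12, or 14 with the +2-day window at 0H.

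The nominal overlap with the last Cohort 1 subject's follow-up is 28 − 14 = 14 to 28 − 7 = 21 days.

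**Illustration of what a written rule could hold.** Assumptions, none of them in the documents: subjects are dosed d days apart in both cohorts; two Cohort 1 subjects have late events, each of the 10 pairs being equally likely; events are found at application + 28 days; only Cohort 2 doses strictly after the second finding count as held. Cohort 1 is dosed at 0, d, …, 4d and Cohort 2 at 4d + g, …, 8d + g. The second finding falls at 28 + jd for j = 1, 2, 3, 4, which arises from 1, 2, 3 and 4 pairs respectively.

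For d = 7 and g = 7, Cohort 2 doses fall on days 35, 42, 49, 56 and 63, and the second finding on day 35, 42, 49 or 56. Doses remaining are 4, 3, 2 and 1. Mean = (1×4 + 2×3 + 3×2 + 4×1)/10 = 20/10 = 2.0.

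For d = 7 and g = 12, doses fall on days 40, 47, 54, 61 and 68. Doses remaining are 5, 4, 3 and 2. Mean = (5 + 8 + 9 + 8)/10 = 3.0.

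For d = 3 and g = 14, doses fall on days 26, 29, 32, 35 and 38, and the second finding on day 31, 34, 37 or 40. Doses remaining are 3, 2, 1 and 0. Mean = (3 + 4 + 3 + 0)/10 = 1.0.

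Mean Cohort 2 doses held, of 5 (range over pairs):

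| Spacing d | g = 7 | g = 12 | g = 14 |
|---|---|---|---|
| 7 days | 2.0 (1–4) | 3.0 (2–5) | 3.0 (2–5) |
| 3 days | 0 | 0.4 (0–2) | 1.0 (0–3) |
| Same day | 0 | 0 | 0 |

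Events that surface earlier, at an unscheduled visit, would leave more doses to hold.

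**The case against.** The strongest reply is that authority to act already exists. The escalation decision is a judgement by the PI and the Medical Monitor, not an automatic result of fewer than two DLTs. Section 8.1 says "Sponsor may stop the study (and/or the study site) for any reason with appropriate notification", and the PI has the same power. Section 11.1.8.1 asks for the eCRF on the day of the visit so that the Sponsor can monitor safety centrally. All of this stands. A reader might infer that late local toxicity would go unrecorded or could not stop dosing; the documents do not support that. What is missing is a criterion that requires review.

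Part of the benefit may be covered already. With 7-day spacing, the first two Cohort 1 subjects reach Day 28 on days 28 and 35, and the last Cohort 1 Day 7 visit is on day 35. The escalation meeting could have that pair's findings. This removes one pair of the ten, and only where spacing is wide.

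Attribution is also hard. Subjects enter at IGA 3, BPO has stopped, other acne therapy is barred until the end of the treatment period, and there is no control arm. A late rise to IGA 4 may simply be the disease. This stands too: a written rule narrows discretion but does not remove it.

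**Conclusion.** The point holds as a gap in the written rules: from Day 9, non-serious local toxicity meets no study-level pause or escalation criterion, and Cohort 2 may be receiving the tenfold dose during that time. It is a cheap improvement to consider, not a defect that undermines the design.

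Its size depends on accrual and on when Cohort 2 is screened. In the illustration it runs from no doses held to a mean of 3.0 of 5, and those doses would be held for review, not necessarily prevented. The spacing, the detection time and the premise of two late events are all assumptions.

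Three stronger readings are not supported. A reader might infer that the 7-day DLT window is itself wrong; for timing escalation after one topical application it is reasonable. A reader might want a probability that late toxicity is missed; the documents give no event rate from which to compute one. A reader might see Section 7.1 as contradicting Section 8.2.2; it concerns individual subjects, and shows only that the protocol already treats a one-point IGA rise as unacceptable for one person.

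**What to change.** Keep the 7-day DLT window for the escalation decision. Add to Section 8.2.2 that, while any subject remains to be dosed, the existing two-subject pause for review also counts subjects who meet a listed criterion at any scheduled or unscheduled visit through Day 28/EOS. The same exclusions for underlying disease and other clear causes should apply.

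The cost is protocol wording; IGA and tolerability are already scored through Day 28. The downside is an occasional unneeded review pause, mainly from late acne flares that are hard to attribute without a control arm. Limiting the rule to the dosing period, and to review and not termination, keeps that cost small.
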